5.1.3 Pharmacokinetic Analysis Set

The PK analysis set will include subjects whose plasma drug concentrations have been measured.

5.1.4 Pharmacodynamic Analysis Set

The PD analysis set will include subjects in whom the extent of DNA hypomethylation in long interspersed nucleotide element-1(LINE-1) has been measured.

6 Considerations for Data Analysis

6.1 Software

The following software (including versions) will be used in the analyses.

- SAS 9.4 (SAS Institute Inc.)

6.2 Data Conversion and Calculation

6.2.1 Conversion of Duration

1 month will be considered with 30 days for the analysis.

6.2.2 Time since Initial Diagnosis

Time since initial diagnosis will be calculated as [the date of first dose of IMP - date of diagnosis]. If the day is missing for date of diagnosis, the 15th of the month is used. If the month is missing, July 1 is used. If the year is missing, the date is left as missing.

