### 7.1.2 Screening Examination

Examination items at screening are listed below. The investigator or subinvestigator will screen subjects who have provided consent based on data collected within 14 days before the start of treatment in Course 1. The use of data collected before informed consent will require the subject’s consent for the use.

The following information collected from the screening examination and the date of examination and measurement will be documented in the medical records and CRF:

Examination items at screeninga

Subject Background	Sex, date of birth, height, diagnosis of AML (WHO classification) and date of the diagnosis, prior treatment for AML (whether or not the subject has undergone hematopoietic stem cell transplantation [if yes, date of transplantation, type of transplantation, ie, bone marrow transplantation, peripheral blood stem cell transplantation, or cord blood transplantation; in case of bone marrow transplantation or peripheral blood stem cell transplantation, type of graft, ie, autograft or allograft] and response to the treatment; whether or not the subject has undergone radiation therapy [if yes, the start and end dates of therapy]; whether or not the subject has received other prior treatment for AML [if yes, type of treatment, the start and end dates of treatment, and regimen]) and response to the treatment, karyotype at screening, cytogenetic abnormalities, extramedullary lesions found after the diagnosis of AML and their sites, (maximum) proportion of blast cells (leukemia cells) in the bone marrow after the diagnosis of AML, diagnosis of malignancies other than AML, date of the diagnosis, treatment provided and date of healing, diagnosis of medically important past illness and date of the diagnosis, and diagnosis of complications found at the time of informed consent and date of the diagnosis
Clinical Symptoms	Subjective symptoms and objective findings
Pregnancy Test b	Urinary or serum HCG
Viral Test	HIV antibody, HBV-DNA, HCV antibody, HBcAB, and HBsAB

Vital Signs	Blood pressure (systolic/diastolic), pulse rate, and body temperature
Twelve-lead ECG and Chest X-ray	Twelve-lead ECG and chest X-ray
Cardiac Function or Respiratory Function c	For cardiac function, LVEF will be measured by echocardiography or MUGA scan. For respiratory function, DLCO or FEV 1 will be measured.

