6.4 Handling of Missing Values and Outliers

No imputation of missing values or exclusion of outliers will be performed.

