8.1 Demographics and Baseline Characteristics

Demographic and other baseline characteristics are as follows;

- 1) Age (< 65 years, ≥ 65 and < 75 years, ≥ 75 years, calculated relative to date of informed consent)
- 2) Sex (Male, Female)
- 3) Height (cm)
- 4) Weight (kg)
- 5) Body surface area (m^2)
- 6) Eastern Cooperative Oncology Group (ECOG) Performance Status (PS) (0, 1 or 2)
- 7) Diagnosis of AML
- 8) Time since initial diagnosis (calculated relative to date of first dose of IMP)
- 9) Hematopoietic stem cell transplantation history (Yes, No) and type of transplantation
- 10) De novo or secondary AML (De novo AML, secondary AML)
- 11) Prior radiotherapy history (Yes, No)
- 12) Chemotherapy history including induction therapy history and consolidation therapy history
- 13) Poor type category of Karyotype at screening (Better risk, Intermediate risk, Poor risk, Unknown)
- 14) Cytogenetic abnormalities (Yes, No, Unknown) and detail of abnormality
- 15) Extra medullary lesions found after diagnosis of AML (Yes, No)
- 16) Maximum proportion of blast cells (leukemic cells) in the bone marrow after diagnosis of AML
- 17) Baseline leukocytes ($\geq 20.0 \times 10^9/L$, ≥ 2.0 and < $20.0 \times 10^9/L$, ≥ 1.0 and < $2.0 \times 10^9/L$, < $1.0 \times 10^9/L$)
- 18) Baseline neutrophil ($\geq 1.0 \times 10^9/L$, ≥ 0.5 and < $1.0 \times 10^9/L$, < $0.5 \times 10^9/L$)
- 19) Baseline platelets ($\geq 50.0 \times 10^9/L$, ≥ 25.0 to < $50.0 \times 10^9/L$, < $25.0 \times 10^9/L$)

1) will be summarized with descriptive statistics in addition to categorical summary. 3), 4), 5), 8) and 16) will be summarized with descriptive statistics. Others will be summarized categorically.

In detail, poor-risk cytogenetics is defined based on the National Comprehensive Cancer Network (NCCN) Guidelines[®] (2014)² as follows:

Risk Status Based on Cytogenetics¹

Risk Status	Cytogenetics
Better-risk	inv(16) ^{2,3} or t(16;16) ² t(8;21) ² t(15;17)
Intermediate-risk	Normal cytogenetics +8 alone t(9;11) Other non-defined
Poor-risk	Complex (≥ 3 clonal chromosomal abnormalities) Monosomal karyotype -5, 5q-, -7, 7q- 11q23 - non t(9;11) inv(3), t(3;3) t(6;9) t(9;22) ⁴

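### SAP 6.2.2 imputes partial diagnosis dates with no upper bound, so an imputed diagnosis can fall after first dose and give a negative time since diagnosis

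*SAP*

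**What the plan says.** SAP 6.2.2 defines time since initial diagnosis as the first-dose date minus the diagnosis date, and gives three rules for incomplete diagnosis dates:

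- Day missing: "If the day is missing for date of diagnosis, the 15th of the month is used".
- Month missing: "If the month is missing, July 1 is used".
- Year missing: "If the year is missing, the date is left as missing".

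The variable is item 8 of the baseline characteristics in SAP 8.1, tabulated by cohort and for Cohorts 1, 2 and 4 together. On the form of summary: "3), 4), 5), 8) and 16) will be summarized with descriptive statistics".

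SAP 6.4 adds a general statement: "No imputation of missing values or exclusion of outliers will be performed". Protocol 11.2 leaves missing-data handling to the SAP. The source item is collected at screening under Protocol 7.1.2: "diagnosis of AML (WHO classification) and date of the diagnosis".

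None of these sections requires the imputed date to fall on or before consent or first dose.

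**The concern.** A diagnosis of AML is an entry condition at screening (Protocol 5.2, criterion 1), so the true diagnosis precedes first dose. The imputation ignores this. If diagnosis and first dose fall in the same month (day missing) or the same year (month missing), the fixed 15th or 1 July can land after first dose, and the subtraction gives a negative disease duration.

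As planned, such a value would enter the mean, SD and minimum of small cohorts. SAP 6.4 offers no correction and, read literally, conflicts with the imputation in 6.2.2. At stake is the credibility of one line in the baseline table: a negative time since diagnosis is plainly an error, and with 3 to 6 subjects one such value visibly shifts the mean.

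**Working it through.** The plan states no figure on this point, so there is nothing to reproduce. The check applies the SAP 6.2.2 rule to possible dates.

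**Inputs**
- Formula and imputed dates: SAP 6.2.2.
- Primary evaluation periods, used as the possible first-dose windows: 1 October 2014 to 31 May 2016 (Cohorts 1, 2 and 4) and 1 September 2016 to 30 November 2017 (Cohort 3), Protocol 15.
- Washout: no chemotherapy in the 2 weeks before the scheduled start of dosing, Protocol 5.2, criterion 7.
- Cohort sizes: 3 to 6 in Cohorts 1, 2 and 4; 6 in Cohort 3, Protocol 3.4.

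**1. Day missing, diagnosis in the month of first dose.** If first dose is on day *d*, the result is *d* − 15. It is negative for *d* = 1 to 14, running from 1 − 15 = −14 to 14 − 15 = −1 days. In all these cases the true gap is at most 14 − 1 = 13 days. A subject given chemotherapy after diagnosis has a gap of at least 14 days, so this branch cannot go negative for that subject.

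**2. Month missing, diagnosis in the year of first dose.** The result is first dose minus 1 July, negative for any dose from 1 January to 30 June.
- 1 January to 1 July: 31 + 28 + 31 + 30 + 31 + 30 = 181 days, or 182 in 2016 (leap year).
- The 2016 limit applies to Cohorts 1, 2 and 4 only; Cohort 3's first January to June is in 2017.
- The washout does not remove this branch. With a 14-day gap, the earliest same-year dose is 15 January, giving −168 days in 2016 or −167 in 2017.

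The limits of −14, −181 and −182 require diagnosis and first dose on the same day, so they are theoretical bounds.

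**3. Sample dates**

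| First dose | Recorded diagnosis | Result under SAP 6.2.2 |
|---|---|---|
| 10 Mar 2015 | Mar 2015 | −5 days |
| 20 Mar 2015 | Mar 2015 | +5 days |
| 10 Mar 2015 | 2015 | −113 days |
| 10 Sep 2015 | 2015 | +71 days |

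**4. Effect on a mean (Cohorts 1, 2 and 4).** Take diagnosis on 2 January 2015 and first dose on 1 February 2015, a true duration of 30 days, with only the year recorded.
- Imputed result: 1 February minus 1 July = −(28 + 31 + 30 + 31 + 30) = −150 days.
- Error for the subject: −150 − 30 = −180 days.
- Shift in the cohort mean: −180/6 = −30 days, or −180/3 = −60 days.
- Shift in the pooled column for Cohorts 1, 2 and 4 (9 to 18 subjects by planned size): −180/9 = −20 to −180/18 = −10 days.

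**5. How much of the calendar is exposed.** All pairs of first-dose date and true diagnosis date (same month or same year, diagnosis on or before dose) were enumerated within each window.

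| Case | Cohorts 1, 2, 4 | Cohort 3 |
|---|---|---|
| Day missing, no minimum gap | 2100/9583 = 21.9% | 1575/7164 = 22.0% |
| Day missing, gap of at least 14 days | 0/2877 | 0/2145 |
| Month missing, no minimum gap | 28099/107817 = 26.1% | 16471/93216 = 17.7% |
| Month missing, gap of at least 14 days | 23619/99473 = 23.7% | 14028/86923 = 16.1% |

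Every date pair counts equally here, which is an assumption. These are shares of calendar combinations, not expected shares of subjects.

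**6. With a cap.** If the imputed date may not exceed consent, and consent does not follow first dose, no result is below 0. In the step 4 example the least favourable case is consent on the day of first dose. The value is then 0 and the mean shifts by (0 − 30)/6 = −5 days or (0 − 30)/3 = −10 days. Values whose imputed date already lies on or before consent do not change.

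**The case against.** The strongest case against is that nothing depends on this variable. It is one baseline descriptor; the SAP plans no tests or intervals (6.5), no covariate adjustment (10.4) and no subgroups (10.5). No partial date is shown to exist, and a recent diagnosis is the kind least likely to lack its month. Data-entry checks and queries (Protocol 10.1), and the discussion of data handling before the final analysis (SAP 4), could catch an impossible value. The specific rule in 6.2.2 can also be read as overriding 6.4, and an impossible date is a derivation error, not an outlier that must be kept.

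Most of this stands and sets the weight of the point. It does not repair the rule: a date that is truly partial in the source cannot be queried into a complete one, and the SAP gives the programmer no alternative to the 15th or 1 July.

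Four stronger readings are tempting but unsupported.
- *Any partial date near enrolment goes negative.* It does not; two of the four sample dates above are positive.
- *The error falls on untreated elderly subjects.* The criterion for those aged 65 or older refers to ineligibility for standard intensive chemotherapy, not to being untreated or newly diagnosed. The 1 July branch can reach any cohort.
- *The median is distorted too.* A recently diagnosed subject is often already the lowest value; making it negative then leaves the median unchanged.
- *The 60-day shift applies throughout.* It needs a cohort of 3, so it cannot arise in Cohort 3, which is planned at 6.

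**Conclusion.** The point holds as a small defect in a stated rule. Followed exactly, SAP 6.2.2 can place diagnosis after first dose, and no section reviewed prevents it. The mid-month branch gives small errors and is closed to subjects given chemotherapy after diagnosis; the 1 July branch is the larger one and is open in every cohort.

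The −30 and −60 day shifts are an illustration. They rest on an assumed true duration of 30 days, a year-only date, and a single affected subject in a cohort of 6 or 3. Whether any value goes negative depends on partial dates whose number the documents do not give; it may be zero. The consequence is limited to the mean, SD and minimum of one descriptive variable. A reader might infer a threat to the tolerability conclusion, but DLT, MTD and efficacy results do not use time since diagnosis.

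**What to change.** Add one sentence to SAP 6.2.2: *If the imputed date is later than the date of informed consent, the date of informed consent is used.* The start of first AML treatment can serve as an earlier bound, but only where that date is complete, since it is a historical date that may itself be partial.

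In SAP 6.4, add *except as stated in 6.2.2* to the statement on imputation, so that the two sections agree.

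The cost is one sentence, one clause and one line of code. The consent date is already recorded (Protocol 7.1.1), as are start dates of prior AML treatment (Protocol 7.1.2). The small downside is that a capped value remains an approximation near zero.

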6.2.3 Complete Remission Rate

Complete remission will be defined as follows.

- Complete remission (CR)

6.2.4 Composite Complete Remission Rate

Composite complete remission will be defined as follows.

- CR
- Complete remission with incomplete platelet recovery (CRp)
- Complete remission with incomplete blood count recovery (CRi)

6.2.5 Overall Remission Rate

Overall remission will be defined as follows.

- CR
- CRp
- CRi
- Partial response (PR)

The investigator or subinvestigator will evaluate response in each course in accordance with the response criteria in following table, which is based on the response criteria for AML treatment established by an international working group¹.

	Bone Marrow	Peripheral Blood
CR	
 Blast cells < 5% 	
 Neutrophil count > 1,000/μL Platelet count \geq 100,000/μL No blast cell Transfusion independence
CRp	
 Blast cells < 5% 	
 Neutrophil count > 1,000/μL Platelet count < 100,000/μL No blast cell Red blood cell (RBC) transfusion independence
Morphologic CRi	
 Blast cells < 5% 	
 Neutrophil count < 1,000/μL No blast cell
PR	
 Rate of decrease in blast cells in the bone marrow \geq 50% and ratio of blast cells of 5% to 25% 	
 Neutrophil count > 1,000/μL Platelet count \geq 100,000/μL No blast cell
Relapse	
 Leukemia cells (blast cells) \geq 5% in the bone marrow or presence of leukemia cells (blast cells) in the peripheral blood are manifested again after CR, CRi, or CRp has been achieved. Leukemia cells with abnormal chromosomes are revealed again in chromosomal testing. 	

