### 5.3 Exclusion Criteria

Patients falling under any of the following criteria at the time of screening will be excluded from this trial:

- 1) Patients with acute promyelocytic leukemia (APL) accompanied by t(15;17)(q22;q12) or (PML/RARA) karyotype abnormalities (including other variant types of APL).

- 2) Patients with multiple cancers (except for adequately treated basal cell or squamous cell skin cancer, in situ cervical cancer, or other cancer from which the subject has been disease free for at least 3 years).
- 3) Patients with life-threatening illnesses other than AML, such as uncontrolled medical conditions or organ system dysfunction which, in the opinion of the investigator or subinvestigator, could compromise the subject's safety or the study outcomes.
- 4) Patients with poorly controlled arrhythmias, or any Class 3 or 4 cardiac disease as defined by the New York Heart Association (NYHA) Functional Classification.
- 5) Patients with symptomatic central nervous system involvement.
- 6) Patients who have received radiation therapy for extramedullary disease within 2 weeks prior to planned enrollment.
- 7) Patients with AEs (other than alopecia) of Grade 2 or higher from prior therapy for AML, at the time of screening for this trial.
- 8) Patients with febrile neutropenia.
- 9) Patients who are human immunodeficiency virus (HIV) antibody positive, hepatitis B virus (HBV)-DNA positive, or with active hepatitis C.
- 10) Patients who have taken any investigational drug or individually imported drug within 2 weeks prior to the scheduled start of IMP administration.
- 11) Patients who have been treated with systemic corticosteroids as treatment for their AML within 2 weeks prior to the scheduled start of IMP administration.
- 12) Patients with uncontrolled active systemic infections.
- 13) Patients who have hypersensitivity to decitabine, SGI-110, or IMP excipients.
- 14) Patients judged to be ineligible by the investigator or subinvestigator for any other reason.

[Rationale for exclusion criteria]

1) Patients with APL will be excluded because it is reported that the remission rate is high in patients treated with all-trans retinoic acid, arsenic trioxide, etc.

2), 5), 6), 10), 11) These criteria have been provided for reasons of subject safety and because the conditions mentioned in these criteria may affect efficacy evaluation.

3), 4), 7) to 9), 12), 13) These criteria have been provided for reasons of subject safety.

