## 7.2.3 Efficacy Evaluation

### 7.2.3.1 Assessment Based on Response Criteria

The investigator or subinvestigator will evaluate response in each course in accordance with the response criteria in [Table 7.2-1](#), which is based on the response criteria for AML treatment established by an international working group, and will document evaluation results in the medical records and CRF. The evaluation results to be documented in the medical records and CRF will be “not evaluable (NE)” when no bone marrow examination has been performed, “progressive disease” when disease clearly progressed without CR, CRi, or CRp achieved after the start of IMP administration, or “no response” when no remission or relapse has been confirmed in the course.

The best overall response for each subject and the date of the first response (CR, CRi, or CRp) will be documented in the medical records and CRF at the time of trial completion or withdrawal from the trial. Also recorded will be the date of the first relapse, if relapse occurred thereafter, and the date of the last evaluation, if no relapse occurred.

Table 7.2-1 Response Criteria		
	Bone Marrow	Peripheral Blood
CR	
 
Blast cells < 5%
 
	
 
Neutrophil count > 1,000/<math>\mu</math>L
 
Platelet count <math>\geq</math> 100,000/<math>\mu</math>L
 
No blast cell
 
Transfusion independence
 

CRp	
 
Blast cells < 5%
 
	
 
Neutrophil count > 1,000/<math>\mu</math>L
 
Platelet count < 100,000/<math>\mu</math>L
 
No blast cell
 
RBC transfusion independence
 

Morphologic CRi	
 
Blast cells < 5 %
 
	
 
Neutrophil count < 1,000/<math>\mu</math>L
 
No blast cell
 

PR	
 
Rate of decrease in blast cells in the bone marrow <math>\geq</math> 50% and ratio of blast cells of 5% to 25%
 
	
 
Neutrophil count > 1,000/<math>\mu</math>L
 
Platelet count <math>\geq</math> 100,000/<math>\mu</math>L
 
No blast cell
 

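### The remission and relapse criteria omit extramedullary leukaemia although such patients may enter, so a remission can be counted while a lesion persists and an extramedullary recurrence is not recorded as a relapse

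*SAP*

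**What the plan says.** **Response.** Protocol 7.2.3.1 states: "The investigator or subinvestigator will evaluate response in each course in accordance with the response criteria in" Table 7.2-1. SAP 6.2.5 repeats the rule (the investigator "will evaluate response in each course in accordance with the response criteria in following table") and the table. Both versions have two criteria columns, bone marrow and peripheral blood. CR, CRp, CRi and PR are built from marrow blasts, neutrophils, platelets, absence of circulating blasts and, for CR and CRp, transfusion independence.

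**Relapse.** The first bullet covers marrow blasts of at least 5% or "presence of leukemia cells (blast cells) in the peripheral blood are manifested again after CR, CRi, or CRp has been achieved". The second reads: "Leukemia cells with abnormal chromosomes are revealed again in chromosomal testing". It names no specimen.

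**Entry.** Protocol 5.3 excludes "Patients who have received radiation therapy for extramedullary disease within 2 weeks prior to planned enrollment" and, separately, patients with symptomatic CNS involvement. No criterion excludes extramedullary leukaemia as such.

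**Data.** Protocol 7.1.2 collects "extramedullary lesions found after the diagnosis of AML and their sites". SAP 8.1 item 15 tabulates this as yes or no.

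**Use.** SAP 6.2.6 ends remission duration at a relapse as the table defines it, or at the last available time point if none is seen. SAP 10.3 and 11.1 split the overall survival curves and the LINE-1 plots by responder status.

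**The concern.** The eligibility criteria and the baseline data show that the sponsor expected some patients with disease outside the marrow. The response rule does not look there. A subject whose marrow clears and whose counts recover is CR by the table even if leukaemia is still present at another site. After remission, a recurrence confined to such a site meets no line of the Relapse row.

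At stake are the complete, composite and overall remission rates, and the two displays that depend on who counts as a responder. Cohorts hold 3 to 6 subjects and no intervals are planned (SAP 6.5), so each classification carries visible weight.

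**Working it through.** There is no plan figure to reproduce, because the point concerns a definition. The check has four steps.

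**1. Does another rule close the gap?**

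| Rule | Where | Covers extramedullary disease? |
|---|---|---|
| CR, CRp, CRi, PR rows | Protocol Table 7.2-1, SAP 6.2.5 | No |
| Relapse, blasts | same | No, marrow and blood only |
| Relapse, chromosomal testing | same | Specimen unstated; does not make an extramedullary recurrence as such a relapse |
| Progressive disease | Protocol 7.2.3.1 | Openly worded, but only for subjects without prior CR, CRi or CRp |
| Withdrawal for apparent progression or relapse | Protocol 9.2 | Could cover it, but is a withdrawal rule and does not define response |

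None of these stops a remission being scored while a lesion persists, or turns a later extramedullary recurrence into a recorded relapse.

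**2. Weight of one subject** (sizes from protocol 3.4). The weight is 100/n.
- n = 3: 33.3 points.
- n = 6: 16.7 points.
- Pooled Cohorts 1, 2 and 4, n = 9 to 18: 11.1 to 5.6 points.

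**3. Chance of at least one false remission in a cohort of 6.** A false remission needs an active lesion, marrow and blood remission, and persistence of the lesion.
- Prevalence p of active lesions: not in the documents. Assumed 5% to 15%.
- Remission probability r: protocol 1.2.2.1.1.2 (reference study SGI-110-01) gives 8/50 = 16% in relapsed or refractory AML and 9/17 = 53% in elderly untreated AML. Pooled, this is (8 + 9)/(50 + 17) = 17/67 = 25%.
- Persistence: assumed to be 1, the worst case. Lesions and remission are assumed independent.

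Formula: 1 − (1 − p × r)^6.

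| r | p = 5% | p = 15% |
|---|---|---|
| 8/50 | 1 − 0.992^6 = 4.7% | 1 − 0.976^6 = 13.6% |
| 17/67 | 1 − 0.9873^6 = 7.4% | 1 − 0.9619^6 = 20.8% |

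The range is about 5% to 21%. Cohort 3 admits only relapsed or refractory subjects (protocol 5.2), so the first row applies there. If a cohort consisted entirely of elderly untreated subjects (r = 9/17), the range would be 15% to 39%. Persistence below 1 lowers every figure.

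**4. Remission duration.** An extramedullary recurrence judged to be apparent progression leads to withdrawal (protocol 9.2), with the examination within 5 days of the decision (protocol 7.1.5). SAP 6.2.6 then takes duration to the last available time point. SAP 10.2 uses plain descriptive statistics, so a relapse date and a last-evaluation date enter in the same way. Few days are added. The recorded status is still wrong: the subject appears not to have relapsed.

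**The case against.** The strongest case against acting is that these are secondary, descriptive endpoints. Cohort transition rests on DLT and safety review, and the criteria were a declared choice: protocol 3.3 adopts the partially modified set used in the reference study. All of that stands, and it limits the importance of the point. It does not explain the omission, because the documents give no reason for leaving extramedullary disease out.

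Four stronger readings are tempting, and the documents do not support them.

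- *Remission duration runs on after an extramedullary relapse.* Withdrawal together with the last-time-point rule probably stops the clock close to the event.
- *A false remission is likely.* With prevalence of 5% to 15%, the chance that a cohort of 6 contains a subject with active lesions is 1 − 0.95^6 = 27% to 1 − 0.85^6 = 62%. That is the chance of enrolling such a subject. A false remission also needs marrow and blood remission and a persisting lesion.
- *The trial already holds lesion status at entry.* Protocol 7.1.2 asks for lesions found at any time after diagnosis, so a yes does not show that a lesion was active at screening.
- *A subject could be CR with no change at all.* No minimum marrow blast percentage is set in protocol 5.2, so the text does not forbid it. It is an extreme hypothetical, and the mandatory screening marrow would reveal it.

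The objection that the remedy needs data outside the CRF also has force. Protocol 7.2.1.1 sends findings to the CRF when they are deemed AEs, and 8.1.1 says progression is not an AE. Clearance of a lesion has no specified CRF field. However, examinations are scheduled throughout the primary evaluation part, and their objective findings go into the medical records (protocol 7.1.4), so a source check is feasible.

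**Conclusion.** The gap is real on the text: extramedullary leukaemia may enter, and no response or relapse row considers it. Remission rates can be overstated and responder status misclassified. The documents do not show that this has happened.

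One affected subject moves a rate by 16.7 points at n = 6 and 33.3 at n = 3. The chance of at least one in a cohort of 6 is about 5% to 21%. That range rests on an assumed prevalence of 5% to 15%, full persistence of lesions, independence, and the reference study's 16% to 25% remission rates. The effect on duration is probably small. DLT is unaffected. The point is worth correcting because the remedy is cheap, but it does not threaten the trial's main conclusion.

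**What to change.** **Where the criteria can still be changed** (protocol Table 7.2-1 and SAP 6.2.5):
- Add to the CR, CRp and CRi rows: no evidence of extramedullary leukaemia on the scheduled examination or on imaging already done.
- Add to the Relapse row: new or recurrent extramedullary leukaemia.

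This is a change to the analysis definitions only. No new imaging is required.

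**For cohorts already past cutoff, or if the table must match the reference study.** Cohorts 1, 2 and 4 had their cutoff on 31 May 2016, before the protocol version of 13 Oct 2017 on which the SAP is based.
- Keep the table and state that extramedullary disease is not considered.
- Flag responders with recorded extramedullary lesions, confirming status at entry and clearance from the medical records.
- Show the remission rates with and without those not documented as cleared.

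**Cost.** A few lines of wording, a source-record check for the few affected subjects, possibly slightly lower remission rates, and, if the rows are changed, a small departure from the reference study's criteria.
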